3.3.2.3 Hepatobiliary Disorders

Elevations of ALT, AST, and bilirubin have been observed during treatment with cabozantinib. It is recommended that subjects with elevation of ALT, AST, and/or bilirubin have more

frequent laboratory monitoring of these parameters. If possible, hepatotoxic concomitant medications should be discontinued in subjects who develop increased values of ALT, AST, or bilirubin.

Subjects on this study may enter with increased ALT/AST serum levels up to $2 \times$ ULN. Dose reductions of study treatment should be considered in any subject who develops drug-related Grade 2 elevated ALT, AST, or bilirubin lasting longer than 1 week. A subject who develops Grade ≥ 3 elevated ALT, AST, or bilirubin should have study treatment held and restarted at a reduced dose (see Table 3-2) after ALT, AST, and bilirubin levels resolve to at least Grade ≤ 1 or baseline. In subjects with recurrence of drug-related Grade ≥ 3 elevated ALT, AST, or bilirubin at the lowest dose level, study treatment should be discontinued. In subjects who develop ALT/AST elevations $> 3 \times$ ULN in combination with a bilirubin elevation $> 2 \times$ ULN without reasonable other explanation, drug-induced liver injury should be suspected and cabozantinib treatment interrupted. Reinstitution of study treatment after recovery of ALT, AST, and bilirubin to Grade 1 or baseline level is at the discretion of the investigator.

3.3.2.4 Hematological Disorders

Hematological toxicities (ie, neutropenia and thrombocytopenia) and associated complications have been observed after administration of cabozantinib and may be managed with dose interruptions and/or dose reductions. Use of granulocyte colony-stimulating factor support for neutrophil recovery is allowed per investigator discretion and in accordance with accepted guidelines after the first incidence of clinically relevant cytopenia.

Complete blood counts with differentials and platelets should be performed regularly. Subjects with hematologic toxicities may require additional or more frequent laboratory tests according to institutional guidelines. Results of such tests are to be forwarded to the local laboratory data management vendor.

Febrile neutropenia or evidence of infection associated with neutropenia must be assessed immediately and treated appropriately and in a timely manner according to institutional guidelines.

Dose reductions or dose interruptions for anemia are not mandated but can be applied as clinically indicated. Supportive care such as red blood cell transfusions may be managed according to institutional guidelines.

3.3.2.5 Fatigue, Anorexia, and Weight Loss

Fatigue has been reported during treatment with cabozantinib. Common causes of fatigue such as anemia, deconditioning, emotional distress (depression and/or anxiety), poor nutrition, sleep disturbance, and hypothyroidism should be ruled out and/or these causes treated in accordance to standard of care. Individual non-pharmacological and/or pharmacologic interventions directed to the contributing and treatable factors should be given. Refer to Table 3-3 for general management guidelines.

Anorexia and weight loss should be managed in accordance to local standard of care including nutritional support. If fatigue, anorexia, or weight loss cannot be adequately managed, study treatment should be temporarily interrupted or dose reduced per Table 3-2 and Table 3-3.

3.3.2.6 Skin Disorders

Palmar-plantar erythrodysesthesia syndrome (PPES; also known as hand-foot syndrome), skin rash (including blisters, erythematous rash, macular rash, skin exfoliation, dermatitis acneiform, and papular rash), pruritus, dry skin, erythema, pigmentary changes, and alopecia have been reported in cabozantinib-treated subjects. All subjects on study should be advised on prophylactic skin care. This includes the use of hypoallergenic moisturizing creams, ointment for dry skin, and sunscreen with sun protection factor ≥ 30 , avoidance of exposure of hands and feet to hot water, removal of calluses, protection of pressure-sensitive areas of hands and feet, and use of thick cotton gloves and socks to prevent injury and to keep the palms and soles dry. Subjects with skin disorders should be carefully monitored for signs of infection (eg, abscess, cellulitis, or impetigo).

Early signs of hand-foot syndrome could be tingling, numbness, and slight redness or mild hyperkeratosis. Early manifestations include painful, symmetrical red and swollen areas on the palms and soles. The lateral sides of the fingers or peri-ungual zones may also be affected. Adequate interventions are required to prevent worsening of skin symptoms such as blisters, desquamations, ulcerations, or necrosis of affected areas. Aggressive management of symptoms is recommended, including early dermatology referral. Treatment guidelines for PPE related to study treatment are presented in Table 3-4.

In the case of study treatment-related skin changes (eg, rash, hand-foot syndrome), the investigator may request that additional assessments be conducted with the subject's consent. These assessments may include digital photographs of the skin changes and/or a biopsy of the affected skin and may be repeated until the skin changes resolve.

Table 3-4: Management of Treatment-Emergent Hand-Foot Syndrome (PPES)

CTCAE v.4.0 Grade	Action To Be Taken
Grade 1	Study treatment may be continued at the current dose if PPES is clinically insignificant and tolerable. Otherwise, study treatment should be reduced to the next lower dose level. ^a Start urea 20% cream twice daily AND clobetasol 0.05% cream once daily. Reassess at least weekly; if PPES worsens at any time or does not improve after 2 weeks, proceed to the intervention guidelines for Grade 2.
Grade 2	Study treatment may be continued if PPES is tolerated. Study treatment should be dose reduced or interrupted if PPES is intolerable. Continue urea 20% cream twice daily AND clobetasol 0.05% cream once daily and add analgesics (eg, NSAIDs/gamma-aminobutyric acid agonists) for pain control if needed. Reassess at least weekly; if PPES worsens or affects self-care, proceed to the intervention guidelines for Grade 3.
Grade 3	Interrupt study treatment until severity decreases to Grade 1 or 0. Continue treatment of skin reaction with clobetasol 0.05% cream twice daily AND analgesics. Resume study drug at a reduced dose if PPES recovers to Grade ≤ 1 . Discontinue subject from study treatment if PPES does not improve within 6 weeks.

CTCAE, Common Terminology Criteria for Adverse Events; NSAID, non-steroidal anti-inflammatory drug; PPES, palmar plantar erythrodysesthesia syndrome.

^a Permitted dose levels are defined by individual protocols.

3.3.2.7 Wound Healing and Surgery

VEGFR inhibitors can cause wound healing complications and wound dehiscence which may occur even long after a wound has been considered healed. Therefore, surgical and traumatic wounds must have completely healed before starting cabozantinib treatment and be monitored for wound dehiscence or wound infection while the subject is being treated with cabozantinib. If possible, cabozantinib treatment should be stopped for at least 28 days prior to major surgery.

3.3.2.8 Hypertension

Hypertension is a common class effect of drugs that inhibit VEGF pathways and has been reported among subjects treated with cabozantinib.

Treatment guidelines for hypertension deemed related to cabozantinib are presented in Table 3-5. Blood pressure should be monitored in a constant position at each visit (either sitting or supine). In general, subjects with known hypertension should be optimally managed before study entry. Decisions to decrease or hold the dose of study treatment must be based on blood pressure readings taken by a medical professional and must be confirmed with a second measurement at least 5 minutes after the first measurement. Other than for hypertension requiring immediate

therapy, the presence of new or worsened hypertension should be confirmed at a second visit before taking therapeutic action. It is recommended that this second visit occurs within 1 week.

Cabozantinib should be discontinued in subjects with hypertensive crises or hypertensive encephalopathy.

Table 3-5: Management of Hypertension Related to Cabozantinib

Criteria for Dose Modifications	Treatment/Cabozantinib Dose Modification
Subjects NOT receiving optimized anti-hypertensive therapy	
> 150 mm Hg (systolic) ^a and < 160 mm Hg OR > 100 mm Hg (diastolic) and < 110 mm Hg	
 Optimize antihypertensive medications by adding new or additional antihypertensive medications and/or increase dose of existing medications. Reduce study treatment by one dose level if optimal antihypertensive therapy (usually to include 3 agents) does not result in BP <150 mm Hg systolic or <100 mm Hg diastolic If subject is symptomatic interrupt study treatment
≥ 160 mm Hg (systolic) OR ≥ 110 mm Hg (diastolic)	
 Reduce cabozantinib by one dose level^b or interrupt study treatment per investigator discretion Add new or additional anti-hypertensive medications and/or increase dose of existing medications and monitor subject closely for hypotension. If optimized antihypertensive therapy (usually to include 3 agents) does not result in BP < 150 mm Hg systolic or < 100 mm Hg diastolic, study treatment should be dose reduced further or interrupted Study treatment should be dose interrupted if upper limits of systolic BP (≥ 160 mm Hg) are sustained and not adequately manageable or if systolic BP is > 180 mm Hg or diastolic BP > 110 mm Hg, or if subject is symptomatic Re-start study treatment at the most tolerable dose and re-escalate only if BP falls to and is sustained at < 150 mm Hg systolic and < 100 mm Hg diastolic
Hypertensive emergency ^c	
 Discontinue study treatment

BP, blood pressure.

^a The investigator may decide to initiate or adjust antihypertensive treatment at a lower threshold than systolic BP >150 or diastolic BP >100 based on their clinical judgment and assessment of the individual subject.

^b Permitted dose levels are defined by individual protocols.

^c Hypertensive emergency is defined as uncontrolled elevated blood pressure with clinical evidence of progressive or impending end-organ damage (eg, myocardial infarction/ischemia, intracranial hemorrhage, cerebral ischemia, pulmonary edema, encephalopathy, kidney damage).

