 - ii. Concurrent uncontrolled hypertension defined as sustained blood pressure (BP) > 150 mm Hg systolic or > 100 mm Hg diastolic despite optimal antihypertensive treatment within 7 days of the first dose of study treatment;
 - iii. Any history of congenital long QT syndrome;
 - iv. Any of the following within 6 months before the first dose of study treatment:
 - unstable angina pectoris;
 - clinically-significant cardiac arrhythmias;
 - stroke (including transient ischemic attack (TIA), or other ischemic event);
 - myocardial infarction;
 - b. GI disorders particularly those associated with a high risk of perforation or fistula formation including:
 - i. Tumors invading the GI tract, active peptic ulcer disease, inflammatory bowel disease (eg, Crohn's disease), diverticulitis, cholecystitis, symptomatic cholangitis or appendicitis, acute pancreatitis or acute obstruction of the pancreatic duct or common bile duct, or gastric outlet obstruction
 - ii. Abdominal fistula, GI perforation, bowel obstruction, intra-abdominal abscess within 6 months before randomization,
Note: Complete healing of an intra-abdominal abscess must be confirmed prior to randomization. Also no pre-existing fistula of head and neck area. No pre-existing ONJ
 - c. Other clinically significant disorders that would preclude safe study participation;
15. Major surgery within 12 weeks before the first dose of study treatment. Complete wound healing from major surgery must have occurred 1 month before the first dose of study treatment. Minor surgery (including uncomplicated tooth extractions) within 28 days before the first dose of study treatment with complete wound healing at least 10 days before the first dose of study treatment. Subjects with clinically relevant ongoing complications from prior surgery are not eligible;

16. QTcF > 500 msec within 1 month before the first dose of study treatment:
 - a. Three ECGs must be performed for eligibility determination. If the average of these three consecutive results for QTcF is \leq 500 msec, the subject meets eligibility in this regard.
17. Pregnant or lactating females;
18. Inability to swallow intact tablets or inability to take pembrolizumab or cabozantinib
19. Previously identified allergy or hypersensitivity to components of the study treatment formulations;

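### Table 3-5's failed-therapy trigger says *or* where *and* is meant, so read literally it misses a patient with only one blood pressure component still raised

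*Combined protocol and SAP*

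**What the plan says.** Table 3-5 in Section 3.3.2.8 has two rows for raised pressure short of an emergency.

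- **Lower-pressure row.** Entry is on systolic above 150 and below 160, "OR > 100 mm Hg (diastolic) and < 110 mm Hg". After therapy is optimised, cabozantinib is reduced by one level if that therapy "does not result in BP <150 mm Hg systolic or <100 mm Hg diastolic". Symptomatic patients are interrupted.
- **Higher-pressure row.** Entry is on systolic of at least 160 or diastolic of at least 110. A one-level reduction or an interruption is directed at once. If optimised therapy then "does not result in BP < 150 mm Hg systolic or < 100 mm Hg diastolic, study treatment should be dose reduced further" or interrupted. A separate line interrupts if systolic values of 160 or more "are sustained and not adequately manageable or if systolic BP is > 180 mm Hg or diastolic BP > 110 mm Hg", or if there are symptoms. On restart, sites may "re-escalate only if BP falls to and is sustained at < 150 mm Hg systolic and < 100 mm Hg diastolic".

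Four other places bear on the point. Section 3.3.2 lists hypertension that stays uncontrolled on best medical management among the reasons to stop cabozantinib permanently. Exclusion criterion 14.a.ii defines uncontrolled hypertension as "sustained blood pressure (BP) > 150 mm Hg systolic or > 100 mm Hg diastolic despite optimal antihypertensive treatment". Section 3.3 lets the investigator reduce or interrupt at lower grades than Table 3-3 specifies. Section 3.3 and Table 3-2 allow one reduction level, from 40 to 20 mg/day.

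**The concern.** A negated *or* is a demanding condition. Failing to reach one target or the other means, strictly, reaching neither. A patient at 155/95 on optimised therapy has reached the diastolic target, so the literal trigger does not fire, although the systolic pressure is still in the range that brought the patient into the row.

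At stake is consistent and safe dosing. Under the literal reading one site could keep that patient at 40 mg/day while the other, reading for intent, reduces to 20 mg/day. The dose-limiting toxicity criteria in Section 2.2.1 also rely on the Section 3.3.2 guidelines to decide when a reduction is needed. The wording could therefore touch the run-in, if failure of optimised therapy were established within the first cycle.

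**Working it through.** The plan gives no figure to reproduce; the check is of logic. Write S for systolic and D for diastolic pressure in mm Hg on optimised therapy.

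**1. The two readings**

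- As written: not (S < 150 or D < 100), which equals S ≥ 150 **and** D ≥ 100.
- With *and*: not (S < 150 and D < 100), which equals S ≥ 150 **or** D ≥ 100.

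They differ exactly when one component is raised and the other is not.

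| Residual pressure | Fires as written | Fires with *and* | Meets re-escalation target |
|---|---|---|---|
| 145/95 | no | no | yes |
| 155/95 | no | yes | no |
| 145/105 | no | yes | no |
| 155/105 | yes | yes | no |

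With *and*, the trigger is the exact complement of the re-escalation target. As written, 155/95 and 145/105 neither trigger action nor qualify for re-escalation.

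**2. Remove what other lines cover**

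The interruption line in the higher-pressure row acts on S ≥ 160 (sustained and unmanageable), S > 180, D > 110, or symptoms. I evaluated both triggers and this line for an asymptomatic patient at every whole-number pressure with S from 100 to 199 and D from 60 to 124. What remains uncovered is:

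- S 150-159 with D < 100; or
- D 100-110 with S < 150. In the lower-pressure row this is 100-109, because 110 enters the higher row.

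This takes any S ≥ 160 on optimised therapy as sustained and not manageable. If a site judged otherwise, the systolic part of the gap in the higher row would run to 180.

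**3. What is lost in each row**

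- Lower: the one-level reduction. The dose may stay at 40 mg/day instead of falling to 20 mg/day.
- Higher: only the further step. A reduction or interruption was already directed on entry.

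**4. Which reading the protocol intends**

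Row entry, the re-escalation line and exclusion criterion 14.a.ii all treat one raised component as loss of control. So does footnote a, which lets investigators begin or adjust treatment "at a lower threshold than systolic BP >150 or diastolic BP >100 based on their clinical judgment". All four fit *and*; none fits the literal *or*.

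**5. Patients at 20 mg**

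Section 2.7 makes 20 mg the minimum dose. The lower row's only failed-therapy action is a one-level reduction, which is not available at 20 mg. Under Section 2.2.1 every later patient would start at 20 mg if the run-in lowers the dose. In the higher row, interruption remains possible.

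**The case against.** The strongest objection is that Section 3.3.2 already goes further than the table. If 155/95 on optimised therapy counts as uncontrolled, as criterion 14.a.ii would have it, then persistence calls for permanent discontinuation, not just a reduction. The rule exists, and it defeats a stronger inference that a reader might draw: that the protocol requires no dose action for such a patient. It does not repair the table, however. Section 3.3.2 states no on-treatment threshold, and 14.a.ii is an eligibility definition, so carrying it over is an inference. If it is carried over, the same pressure requires nothing under the literal trigger and permanent discontinuation under Section 3.3.2, with the step to 20 mg skipped. The two need reconciling.

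Second, many clinicians will read the bullet as missing either target, and the surrounding lines steer them there. Table 3-5 is presented as guidance, there are at most two sites, and Section 26 provides weekly teleconferences that cover toxicity. This stands: harm depends on a literal reading, and divergence between sites is a possibility, not an expectation.

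Third, Section 3.3 allows earlier action at the investigator's discretion. It permits action but does not require it. Table 3-3 might also apply. Its note sends specific conditions to Section 3.3.2, and whether its Grade 3 row would reach these pressures depends on CTCAE thresholds that the documents do not reproduce. I leave that open.

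Fourth, a reader might infer that the higher row's instruction is unworkable at 20 mg. It is not, because interruption is offered as the alternative. The difficulty at 20 mg lies mainly in the lower row.

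**Conclusion.** The wording error is real and occurs in both rows. Read literally, it leaves an asymptomatic patient with one raised component, within the ranges shown above, with no required reduction in the lower row and no required further step in the higher row. The dose consequence in the lower row is 40 rather than 20 mg/day.

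The conclusion rests on a literal reading of the bullets and on treating systolic values of 160 or more on optimised therapy as caught by the interruption line. It does not extend to the protocol as a whole, because Section 3.3.2 has a discontinuation rule, though one without a threshold.

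A reader might try to turn the hypertension rates in Section 1.2.3.2.1 into a number of affected patients among the 34. The documents do not support that. The rates are pooled single-agent figures, and nothing gives the share of patients left with exactly one raised component after optimised therapy. I therefore give no count.

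This is a drafting inconsistency in a safety table that should be corrected. It does not bear on the response-rate endpoint, the sample size or the analysis.

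**What to change.** 1. In both failed-therapy bullets of Table 3-5, replace *or* with *and*, so that therapy has succeeded only when systolic is below 150 **and** diastolic is below 100.
2. Add a cross-reference from Table 3-5 to the permanent-discontinuation list in Section 3.3.2, stating how the two steps relate: when failure of optimised therapy leads to a reduction or hold, and when it counts as persistent and uncontrolled. This should be required, since the first change alone leaves the two rules unreconciled.
3. State that a patient already at 20 mg is interrupted, because no lower level exists. This matters mainly in the lower-pressure row. Section 3.3.1.1 already allows restart at 20 mg after a hold if judged safe.

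The cost is one word in each of two bullets, one cross-reference and one sentence. The clinical downside is a few more mandated reductions or holds. Visits, data collection and sample size are unchanged.

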3.3.2.9 Thromboembolic Events

Thromboembolic complications are frequent in cancer patients due to procoagulant changes induced by the malignancy or anticancer therapy including inhibitors of VEGF pathways. Deep vein thrombosis and PE have been observed in clinical studies with cabozantinib; including fatal events (please refer to the Investigator's Brochure). Subjects who develop a PE or DVT should have cabozantinib treatment held until therapeutic anticoagulation with heparins (eg, low molecular weight heparin [LMWH]) is established. LMWH are the preferred management for thrombotic events, warfarin is not recommended. Cabozantinib treatment may be resumed in subjects who are stable and have uncomplicated PE or DVT and are deriving clinical benefit from cabozantinib treatment and that anticoagulation does not place them at a significant risk that outweighs the benefit of resuming treatment per discretion of the investigator/Sponsor. During anticoagulation treatment, subjects need to be monitored on an ongoing basis for bleeding risk and signs of bleeding which may require additional or more frequent laboratory tests in accordance to institutional guidelines. If there are any signs of clinically significant bleedings, cabozantinib treatment should be permanently discontinued.

Arterial thrombotic events (eg, transient ischemic attack, myocardial infarction) have been observed in studies with cabozantinib. Subjects should be evaluated for preexisting risk factors for arterial thrombotic events such as diabetes mellitus, hyperlipidemia, hypertension, coronary artery disease, history of tobacco use, and cardiac or thromboembolic events that occurred before initiation of study treatment. Cabozantinib treatment should be discontinued in subjects who develop an acute myocardial infarction, cerebral infarction or any other clinically relevant arterial thromboembolic complication.

3.3.2.10 Proteinuria

Proteinuria is an anticipated AE with the inhibition of VEGF pathways and has been observed in cabozantinib clinical studies, and nephrotic syndrome has been reported with cabozantinib and other inhibitors of VEGF pathways. Management guidelines are provided in Table 3-6.

Cabozantinib should be permanently discontinued in subjects who develop nephrotic syndrome (proteinuria > 3.5 grams per day in combination with hypoalbuminemia and peripheral edema [hyperlipidemia and thrombotic disease may also be present]) or any other relevant renal disease.

Table 3-6: Management of Treatment-emergent Proteinuria

Severity of Proteinuria (UPCR)	Management of Proteinuria
≤ 1 mg/mg (≤ 113.1 mg/mmol)	
• No change in cabozantinib treatment or monitoring
> 1 and < 3.5 mg/mg (> 113.1 and < 395.9 mg/mmol)	
• Consider confirming with a 24-hour protein assessment within 7 days• No change in cabozantinib treatment required if UPCR ≤ 2 mg/mg or urine protein ≤ 2 g/24 hours on 24-hour urine collection.• Dose reduce or interrupt cabozantinib treatment if UPCR > 2 mg/mg on repeat UPCR testing or urine protein > 2 g/24 hours on 24-hour urine collection. Continue cabozantinib on a reduced dose if UPCR decreases to < 2 mg/mg. Consider holding cabozantinib treatment if UPCR remains > 2 mg/mg despite a dose reduction until UPCR decreases to < 2 mg/mg. Restart cabozantinib treatment at a reduced dose after a dose hold unless otherwise approved by sponsor.• Repeat UPCR within 7 days and once per week. If UPCR < 1 mg/mg on 2 consecutive readings, UPCR monitoring can revert to protocol-specific times. (Second reading is confirmatory and can be done within 1 week of first reading.) If UPCR remains > 1 mg/mg and < 2 mg/mg for 1 month or is determined to be stable (< 20% change) for 1 month, check urine protein/creatinine per protocol or as clinically indicated.
≥ 3.5 mg/mg (≥ 395.9 mg/mmol)	
• Hold cabozantinib treatment pending repeat UPCR within 7 days and/or 24-hour urine protein.• If ≥ 3.5 mg/mg on repeat UPCR, continue to hold cabozantinib treatment and check UPCR every 7 days. If UPCR decreases to < 2 mg/mg, restart cabozantinib treatment at a reduced dose and monitoring of urine protein/creatinine should continue weekly until the UPCR decreases to < 1 mg/mg. If UPCR remains > 1 mg/mg and < 2 mg/mg for 1 month or is determined to be stable (< 20% change) for 1 month, check urine protein/creatinine per protocol or as clinically indicated.
Nephrotic syndrome	
• Discontinue all study treatment

UPCR, urine protein/creatinine ratio.

